Given: (a) the relationship between psychological well-being and physical activity, (b) the potential for combined PP and behavioral interventions to improve physical activity more than either alone, and (c) the great need for effective activity interventions in T2D patients, the use of a combined PP and MI intervention has the potential to increase physical activity and reduce adverse events in a high-risk, high-yield population of patients. This would have direct benefits to patients and would impact public health, given that >18 million Americans have T2D. This project could represent a key first step in determining the feasibility and efficacy of such a program.

II. Specific aims. In a randomized trial of 60 T2D patients with low baseline physical activity, our goal is to complete the following specific aims:

Specific Aim 1 (feasibility and acceptability): To determine whether the PP-MI intervention is feasible (assessed by % of total PP-MI phone sessions completed) and well-accepted (assessed by participant ratings of the ease and utility of each PP-MI session) among T2D patients with low baseline activity.

Specific Aim 2 (physical activity): To assess whether PP-MI is associated with larger increases in moderate to vigorous physical activity (MVPA), and less sedentary time, on accelerometer at 8 and 16 weeks, compared to standard MI.

Specific Aim 3 (additional outcomes): To explore whether the PP-MI intervention is associated with greater improvements on other psychological, behavioral, and medical outcomes, compared to MI.

Hypotheses: Our primary hypotheses are that a majority of the PP-MI participants (n=30) will fully complete at least 6 of 8 PP-MI sessions (feasibility) and provide mean ratings of over 7/10 for the ease and utility of PP-MI sessions (acceptability). We also expect participants in PP-MI to have larger improvements in MVPA (minutes/day) and other key outcomes, warranting further testing in a well-powered efficacy trial.

III. Subject selection

A. Inclusion/exclusion criteria

Inclusion criteria. We will enroll adults who are seen in an outpatient clinic at MGH (including the MGH Diabetes Center) and meet the following criteria:

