All analyses will be performed under the direction of biostatistician [name]. All analyses will be performed using Stata 14.0. Alpha for between-group comparisons will be set at $p=.05$. We will use descriptive statistics (means, standard deviations, proportions for the Aim 1 feasibility/acceptability outcomes. For Aim 2, we will compare between-group improvement from baseline in mean minutes/day of MVPA (and sedentary time) at 8 weeks using a random effects regression model, with a random intercept for each patient, allowing us to include participants with some missing data.¹⁰¹ For Aim 3, we will likewise compare change from baseline on all measures (e.g., self-care, A1C) at 8 weeks, using random effects models. We will secondarily compare outcomes at 16 weeks, and will complete sensitivity analyses by sex. All variables used in minimization (age, gender, baseline MVPA, Charlson index) will be included as covariates in these models as per protocol using this method.⁶⁰ We will also measure pre-post effect size (Cohen's d , defined as change in the outcome measure divided by the standard deviation of the measure across all time points) of PP-MI for each Aim 2/3 outcome. If there are significant between-group differences in physical activity outcomes, we will use mediation analyses¹⁰² to evaluate a pathway from PP-MI to proximal targets (positive affect/optimism/self-efficacy) to physical activity.

D. Power analysis

For our primary aim (feasibility/acceptability), in our prior work, 75% of subjects completed three-quarters of sessions.^{25,35} Using the same rate, with 30 PP-MI participants we will have 80% power (two-sided $\alpha=0.05$, binomial proportion test) to demonstrate that the proportion who complete ≥ 8 of 11 PP-MI sessions is larger than 50% (i.e., a majority). Likewise, mean PP ease/utility scores were 7.8 \pm 1.8 in prior work;³⁵ with $n=30$ (and 4 weekly ratings per participant), we will have 93% power (using a within-person correlation of 0.5 for ratings across exercises) to detect a true mean score of >7.0 on composite ratings. This initial trial is not powered to definitively test group differences on physical activity and other Aim 2/3 outcomes, but it will allow us to gather data on PP-MI's impact on these outcomes at this key early stage.

VII. Risks and discomforts

A. Complications of surgical/non-surgical procedures

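### Section VI.C plans only descriptive statistics for the primary aim, while VI.D justifies 30 PP-MI participants by the power of tests that VI.C does not include, and the ratings test is not named at all

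*Combined protocol and SAP*

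**What the plan says.** Section II (Hypotheses) puts the primary hypotheses in words, with no test: "Our primary hypotheses are that a majority of the PP-MI participants (n=30) will fully complete at least 6 of 8 PP-MI sessions (feasibility"), and they will "provide mean ratings of over 7/10 for the ease and utility of PP-MI sessions (acceptability").

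Section VI.C gives the analysis of these outcomes in one sentence: "We will use descriptive statistics (means, standard deviations, proportions for the Aim 1 feasibility/acceptability outcomes". Its only significance level is restricted in scope: "Alpha for between-group comparisons will be set at" .05. Aim 1 is a question about the PP-MI arm alone, so that level does not reach it.

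Section VI.D calls feasibility/acceptability the primary aim and bases 30 PP-MI participants on two power statements:

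- **Feasibility.** 80% power, two-sided alpha 0.05, "binomial proportion test) to demonstrate that the proportion who complete" at least "8 of 11 PP-MI sessions is larger than 50% (i.e., a majority"). The assumed rate is 75%.
- **Acceptability.** 93% power, "using a within-person correlation of 0.5 for ratings across exercises", "to detect a true mean score of >7.0 on composite ratings". The assumed mean is 7.8 with SD 1.8, with 4 weekly ratings per participant. No test, alpha or sidedness is stated.

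Section VI.D also counts completers on a different scale (8 of 11 sessions) from Section II (6 of 8).

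**The concern.** Power is a property of a specified test. If Aim 1 is only summarised, the 80% and 93% describe no analysis in the plan. The two aspects differ in degree. For feasibility, VI.D does name the test, level, sidedness and null value, and the gap is that VI.C does not adopt them. For the ratings, neither section names a test, so the 93% cannot be tied to any analysis.

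At stake is how the primary aim is concluded. A majority in the sense of Section II is reached at 16 of 30, whereas the test behind the sample size needs more. The plan does not say which reading governs, and this should be settled before the data are seen. The two completer definitions add to the problem, because a test needs a single endpoint.

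**Working it through.** **Feasibility: reproducing the 80%**

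Inputs from VI.D: n = 30, null rate 0.50, assumed rate 0.75, two-sided alpha 0.05. I use the exact binomial, with the two-sided p-value taken as twice the upper tail.

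- 20 completers: P(X ≥ 20 | 0.5) = 0.0494, two-sided p = 0.099. Not significant.
- 21 completers: P(X ≥ 21 | 0.5) = 0.0214, two-sided p = 0.043. Significant, so the cut-off is 21 of 30.
- Power: P(X ≥ 21 | 0.75) = 0.803, which matches the stated 80%.

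**Where a bare majority and the test disagree**

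| Completers | Two-sided p | Two-sided 95% Clopper-Pearson interval |
|---|---|---|
| 16/30 | 0.86 | 34% to 72% |
| 20/30 | 0.099 | 47% to 83% |
| 21/30 | 0.043 | 51% to 85% |

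- If the true rate is 50%: P(X ≥ 16) = 0.428, against 0.021 for X ≥ 21.
- If the true rate is 75%: P(16 ≤ X ≤ 20) = 0.997 − 0.803 = 0.194. The two readings would disagree about one time in five under VI.D's own assumption.

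The cut-off depends on the arm size, and minimization (Section IV.C) need not give exactly 30 per arm. By the same rule it is 20 of 28, 21 of 29, 21 of 30, 22 of 31 and 23 of 32.

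**Acceptability: trying to reproduce the 93%**

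Inputs from VI.D: mean 7.8, reference value 7.0 (difference 0.8), SD 1.8, within-person correlation 0.5, n = 30. I take 1.8 as the SD of a single rating. With m ratings averaged per participant:

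SD of a participant's mean = 1.8 × √[(1 + (m − 1) × 0.5)/m]; SE = SD/√30; noncentrality = 0.8/SE.

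For m = 4: SD = 1.8 × √(2.5/4) = 1.423, SE = 0.260, noncentrality = 3.08.

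The documents do not state m. VI.D mentions 4 ratings. Eight would be one composite for each of 8 sessions (my assumption). Thirty-two is 4 ratings per session (Section V.E) over 8 sessions. At alpha 0.05:

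| m | SD of mean | SE | Two-sided t | Two-sided z | One-sided t | One-sided z |
|---|---|---|---|---|---|---|
| 4 | 1.423 | 0.260 | 84.5% | 86.9% | 91.3% | 92.4% |
| 8 | 1.350 | 0.246 | 88.0% | 90.1% | 93.6% | 94.5% |
| 32 | 1.293 | 0.236 | 90.6% | 92.4% | 95.2% | 96.0% |

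Figures near 93% arise from a one-sided test with few ratings averaged, or from a two-sided normal approximation with many. The text does not identify which was used.

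For a two-sided t-test, the sample mean would have to exceed 7 + 2.045 × SE: 7.53 (m = 4), 7.50 (m = 8) or 7.48 (m = 32). An observed mean just over 7 would not be enough.

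**The case against.** The strongest reply is that VI.C and VI.D are adjacent subsections of one document. VI.D gives the whole feasibility test and its 80% reproduces, and VI.C does not say that nothing beyond summaries will be done. A reader can take VI.D's test as the intended inference. This is a pilot, and descriptive reporting of feasibility is legitimate in a pilot. Much of this stands. For feasibility the gap is that the analysis section does not adopt a test specified next door, and descriptive reporting alone would not be a fault had no power been claimed for tests.

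The reply does not cover the ratings. The word that links the two power statements in VI.D (likewise) might be read as carrying over the two-sided 0.05. That is not stated, leaves the test unnamed, and does not give 93% with 4 ratings (84.5% or 86.9%).

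Three stronger readings are tempting but unsupported:

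- A reader might infer that the protocol declares success at a bare majority or at any mean above 7. It does not; it leaves the decision rule open.
- A reader might infer that the 93% is wrong. It is reachable under some choices; the fault is that the choices are not stated.
- A reader might take 1.8 as the SD of participant means, which would put the power far lower. VI.D's use of a within-person correlation speaks against this, because that correlation has no role unless individual ratings are being averaged.

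**Conclusion.** The point holds as a minor-to-moderate inconsistency that should be fixed. The plan's only sample-size justification rests on two tests that its analysis section does not include, and one of them is named nowhere. For feasibility, 21 of 30 is needed rather than 16, and results of 16 to 20 have no defined interpretation. For acceptability, two-sided t power is about 85% to 91% for 4 to 32 ratings averaged (z: 87% to 92%), against a stated 93%.

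These figures assume exactly 30 PP-MI participants, the exact binomial test, 1.8 as the SD of one rating, and a common correlation of 0.5 between any two ratings from the same participant. The trial's size is not called into question.

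**What to change.** 1. **Completer definition.** Reconcile 6 of 8 (Section II) with 8 of 11 (VI.D), so that hypothesis, analysis and power use one threshold consistent with the number of sessions delivered.
2. **VI.C, feasibility.** Keep the descriptive summaries. Add VI.D's binomial test as an exact two-sided 5% test against 50% in all participants randomised to PP-MI, with the two-sided 95% Clopper-Pearson interval. State the cut-off of 21 of 30, to be recomputed if the arm is not exactly 30.
3. **VI.C, acceptability.** Add a two-sided one-sample comparison of participant-level mean composite ratings with 7.0, with its 95% confidence interval. Report how many participants gave no ratings, since they cannot contribute to this mean.
4. **VI.D.** State the ratings test, its sidedness and the number of ratings averaged. Confirm that 1.8 is the SD of a single rating, and restate the 93% to match.

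The cost is a few sentences. The bar becomes 21 rather than 16 of 30, and the stated power for the ratings will probably be slightly lower. Sample size and data collection do not change.

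### If the three visits share one model, a random intercept alone gives the 8- and 16-week contrasts one pooled variance, and the secondary 16-week test could run at roughly 6–10% instead of 5%

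*Combined protocol and SAP*

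**What the plan says.** The trial is small: "In a randomized trial of 60 T2D patients with low baseline physical activity", planned as 30 per arm (Section IV.C). Aim 2 concerns MVPA and sedentary time "on accelerometer at 8 and 16 weeks, compared to standard MI".

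Section VI.C sets alpha at .05 for comparisons between arms. The main Aim 2 comparison, at 8 weeks, is made "using a random effects regression model, with a random intercept for each patient, allowing us to include participants with some missing data". For the other outcomes: "For Aim 3, we will likewise compare change from baseline on all measures (e.g., self-care, A1C) at 8 weeks, using random effects models". The later visit gets one clause: "We will secondarily compare outcomes at 16 weeks". On covariates: "All variables used in minimization (age, gender, baseline MVPA, Charlson index) will be included as covariates in these models".

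The section gives no random slope, residual covariance structure, robust standard error or degrees-of-freedom method. It does not say whether weeks 8 and 16 come from one fit or two, or whether baseline is a response row as well as a covariate.

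Table 1 schedules self-report and accelerometry at enrollment, week 8 and week 16, but weight and A1C only at enrollment and week 8. The physical activity paragraph of Section V.E gives accelerometry at baseline and 8 weeks only, which conflicts with Table 1 and with the visit descriptions in Section V.A.

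**The concern.** A random intercept with independent residuals implies equal variance at every visit and one common correlation between any two visits. With three visits in one such model, the baseline-to-8 and baseline-to-16 contrasts have the same model variance.

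Equal correlation is doubtful in this design. Week 16 is twice as far from baseline as week 8, and only the two later visits follow the intervention. The week-8 assessment is in person, whereas at week 16 self-report is by phone and the device is mailed. If correlation with baseline weakens over time, the 16-week change varies more than the model allows, so its interval is too narrow and its test rejects too often. The 8-week interval is then usually too wide.

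The results are meant to show whether a larger efficacy trial is warranted, so interval width matters. Section VI.C also makes mediation analyses conditional on a significant physical activity difference without naming the visit, so a false 16-week signal could carry forward.

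**Working it through.** **Inputs from the documents:** alpha .05 (taken as two-sided), 30 per arm, random intercept only, follow-up at 8 and 16 weeks. **Assumed:** outcome correlations, because the documents give none (the 0.5 in Section VI.D is for session ratings), equal variances, complete data and no arm effect. Let r8 and r16 be the correlations of weeks 8 and 16 with baseline, and s the correlation between weeks 8 and 16.

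**Version A: baseline, week 8 and week 16 all as response rows.**
- Model variance of either change, in units of the outcome variance: 2(1 − mean of r8, r16 and s).
- True variances: 2(1 − r8) and 2(1 − r16).
- Actual error rate: 2[1 − Φ(1.96 × √(model/true))].

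*The plan's 5%.* With all correlations .6, the model variance is 2(1 − .6) = .80 and both true variances are .80. The ratio is 1 and the error is 5.0%, so the stated alpha is reproduced when correlations are equal.

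*Steep decay, (r8, r16, s) = (.7, .49, .7).* The mean correlation is .63, so the model variance is 2(.37) = .74.
- Week 8: true variance .60, √(.74/.60) = 1.11, error 3.0%.
- Week 16: true variance 1.02, √(.74/1.02) = .85, error 9.5%.

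**Version B: baseline as covariate, weeks 8 and 16 as the only response rows.** With a common slope b = (r8 + r16)/2, the true residual variance at visit t is 1 − 2·b·rt + b², and the model uses the average of the two. For the same pattern, b = .595, the residual variances are .521 and .771, and their average is .646.
- Week 8: √(.646/.521) = 1.11, error 2.9%.
- Week 16: √(.646/.771) = .915, error 7.3%.

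**Version C: change scores as the two response rows.** The model uses the average of the two true change variances. For the same pattern this is (.60 + 1.02)/2 = .81.
- Week 8: √(.81/.60) = 1.16, error 2.3%.
- Week 16: √(.81/1.02) = .89, error 8.1%.

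**Decaying patterns, error at week 8 / week 16:**

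| (r8, r16, s) | A: baseline as response row | B: baseline as covariate | C: change scores |
|---|---|---|---|
| (.5, .25, .5) | 3.4% / 8.4% | 3.8% / 6.3% | 2.8% / 7.4% |
| (.7, .49, .7) | 3.0% / 9.5% | 2.9% / 7.3% | 2.3% / 8.1% |
| (.8, .64, .8) | 2.7% / 10.0% | 2.5% / 7.8% | 2.0% / 8.4% |
| (.7, .60, .7) | 3.9% / 7.4% | 3.8% / 6.3% | 3.4% / 6.7% |
| (.7, .65, .7) | 4.4% / 6.2% | 4.3% / 5.7% | 4.1% / 5.9% |

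**Simulation check.** With 20,000 trials per pattern and version A fitted by REML with t tests, the first three rows gave 3.7/8.5%, 2.9/9.7% and 2.6/9.9%. When each contrast used its own variance, as in separate fits per visit, error stayed at 4.7–5.3% at week 8 and 5.0–5.2% at week 16.

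**Follow-ups closer to each other than to baseline.** For (.5, .5, .8) in version A, the model variance is 2(1 − .6) = .80 and both true variances are 1.00. The ratio is √.80 = .894, so error is 8.0% at both visits. For (.6, .5, .8), week 8 is 6.1% and week 16 is 9.3%. In versions B and C, (.5, .5, .8) gives exactly 5.0% at both visits, because the two follow-up variances are equal.

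**Power at week 8.** Take an effect with 79% power under the correct variance, so the standardized effect is 1.96 + .81 = 2.77. In version A with (.7, .49, .7), the effective cut-off is 1.96 × 1.11 = 2.18, and power is Φ(2.77 − 2.18) = Φ(.59) = 72%.

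**The case against.** The strongest objection is that the joint fit is not written down. Section VI.C describes an 8-week comparison and then, in another sentence, a 16-week one. Two separate baseline-plus-one-visit models fit that wording, and under them both tests stay near 5%. This stands. The joint fit is the likelier reading, because the stated reason for the model is to keep patients with partial data, and a patient missing the one follow-up in a separate fit contributes little beyond a baseline row. It remains an inference.

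A reader might infer that the 16-week test rejects about twice as often as stated. That needs steep decay together with baseline as a response row. Milder decay, or baseline as a covariate or in change scores, gives about 6–8%, and no documented correlation settles which applies.

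A reader might also infer that the main 8-week comparison is inflated. Under decay alone it is usually conservative. Inflation to about 6–8% needs baseline as a response row and follow-ups that correlate more strongly with each other than with baseline. Section VI.C lists baseline MVPA as a covariate, so that arrangement cannot be presumed.

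Finally, Section VI.D says the trial is not powered for definitive tests on Aims 2 and 3. The primary aim, feasibility and acceptability, and its sample size are untouched. This limits the severity of the point.

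**Conclusion.** The point holds as a minor, inexpensive improvement. The plan names a within-patient structure that is valid for both visits in a joint fit only under equal variances and equal correlations. If the visits are fitted jointly and correlation with baseline falls over time, the secondary 16-week test runs at roughly 6–10% instead of 5%, and the 8-week test usually at about 2–4.5% with some loss of power.

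These sizes rest on assumed correlations, equal variances, complete data and 30 per arm; the effect of dropout was not assessed. The documents do not support saying that the plan certainly pools the visits, that error doubles whenever correlation declines, or that every Aim 3 outcome is affected. A1C and weight have no week-16 value to pool.

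**What to change.** In Section VI.C, for outcomes measured at three visits, replace the random-intercept-only structure with text such as: *Weeks 8 and 16 will be analyzed in one linear mixed model for repeated measures, with visit as a categorical factor, arm-by-visit terms, an unstructured within-patient covariance and small-sample degrees of freedom. If this fails to converge, a random intercept with patient-clustered robust standard errors will be used.*

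Also state how baseline enters, and let the outcome's own baseline enter once only:
- as a covariate, with weeks 8 and 16 as the responses; or
- as a response row, in which case baseline MVPA is dropped as a covariate from the MVPA model, where it would otherwise be both response and predictor.

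Reconcile the accelerometer schedule in Section V.E with Table 1, so that it is clear MVPA and sedentary time have a week-16 value.

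The cost is a few sentences and a different covariance option, with no new data or patients. An unstructured covariance has six parameters over three response visits, or three over two, against two for the random intercept. The 16-week interval will usually be slightly wider. If correlations and variances are in fact equal, error stays near 5% either way.
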